These inclusion and exclusion criteria were selected based on AACVPR/ACC/AHA guidelines and previously published protocols.

**Overview of Study Design:** Patients who meet all eligibility criteria and provide consent will be enrolled into the study and randomized (1:1) to THCR (n=20) or traditional clinic-based CR (n=20). After randomization, each group will initiate the program to which they are allocated, wherein the first intervention visit for each group will be a clinic-based CR session. Each program will include 24 CR sessions over the course of 3-months. As part of standard of care, all patients will complete a six-minute walk test [6MWT], modified Balke Treadmill test, sit-to-stand test, PHQ-9, and Duke Health Profile (DUKE) questionnaire upon program completion (3-month follow up visit).

**Sample Size and Power Estimates:** Although some have used pilot studies to estimate effect sizes for primary outcomes, I agree with leaders in our field who argue that effect size estimates from small pilot studies are too imprecise to meaningfully inform effect size assumptions of power analyses for larger, later stage

studies. Therefore, I do not provide power calculations for the effects of our intervention on adherence and behavioral health outcomes. I will, however, use estimates from these studies (e.g., standard deviations, attrition rates) to help determine an appropriate sample size for a subsequent study that is adequately powered to detect meaningful improvements in measures of adherence, functional capacity, and health-related quality of life

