Tertiary	% of participants who complete outcome assessments upon program completion in each arm	Participants who complete outcome assessments upon program completion will be tallied. Numerator= total # of participants randomized into each arm who complete outcome assessments upon program completion.  Denominator= total # of participants randomized into each arm.
Tertiary	Mean % of CR sessions administered as intended in each arm	% of CR sessions (out of all 24 sessions) administered as intended to participants allocated to the THCR intervention and, separately, the traditional CR intervention
Tertiary	# of eligible patients referred to CR/month	# of patients who are referred to CR and eligible for the pilot study per month
Tertiary	% of participants who report adequate acceptability of the THCR intervention	% of participants who report an average score ≥4 (agree or completely agree) for their rating of the patient-perceived THCR intervention's feasibility on the four-item Acceptability of Intervention Measure (AIM). All four items of the AIM are rated on a Likert response scale ranging from 1 to 5 with higher scores indicating greater acceptability. Each Likert response scale rating will be summed (minimum: 4, maximum: 20) and averaged (minimum: 1, maximum: 5) across all four items.
Tertiary	% of participants who report adequate appropriateness of the THCR intervention	% of participants who report an average score ≥4 (agree or completely agree) for their rating of the patient-perceived THCR intervention's feasibility on the four-item Intervention Appropriateness Measure (IAM). All four items of the FIM are rated on a Likert response scale ranging from 1 to 5 with higher scores indicating greater appropriateness. Each Likert response scale rating will be summed (minimum: 4, maximum: 20) and averaged (minimum: 1, maximum: 5) across all four items.
Exploratory	Change in total distance traveled in 6MWT	This is to measure pre-to-post program change in functional capacity (using the six-minute walk test [6MWT]) among THCR and, separately, traditional CR participants. The 6MWT is a sub-maximal exercise test used to assess aerobic capacity and endurance. The total distance (meters) traveled over a time period of six minutes is used as the outcome by which to compare changes in performance capacity.

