Exploratory	Change in health-related quality of life score	This is to measure pre-to-post program change in health-related quality of life (Duke health profile questionnaire [DUKE; physical, mental, social, and general health composite scores]) among THCR and, separately, traditional CR participants. The DUKE is a 17-item self-report questionnaire for measuring generic health-related quality of life over a 1-week time period. Responses are scored to calculate physical health, mental health, and social health scores, which are then summed and divided by 3 to obtain a general health score. The general health score ranges from 0 - 100, with high scores indicating better health-related quality of life.

I will use EHR and eCC data to assess feasibility metrics relevant to recruitment, retention, outcome assessments (described below), adherence, and fidelity to both the hybrid CR and traditional CR intervention. Survey data from the FIM, AIM, and IAM will be used to assess patient-perceived intervention feasibility, acceptability, and appropriateness, respectively. Data will be extracted from these sources via Trac requests, patient notes, patient chart review, and data export. Quality of administration will be assessed using direct observations throughout the trial, wherein research personnel will observe CR sessions (including onboarding sessions) and fill out a pragmatic checklist to assess fidelity. *Feasibility Criteria*. Feasibility will be achieved if the following criteria are met: (1) ≥3 eligible ACS patients are enrolled/month (recruitment); (2) ≥70% of THCR, and separately, traditional CR participants attend ≥1 CR sessions after randomization (program initiation); (3) ≥70% of THCR, and separately, traditional CR participants complete outcome assessments at 3 month follow up; (4)

 $\geq$ 50% of CR sessions ( $\geq$ 12 of 24) are completed by those allocated to each arm (adherence); (5)  $\geq$ 80% of CR sessions ( $\geq$ 20 of 24) are administered as intended for each arm (fidelity).

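### The fidelity criterion gives its minimum as both 80% and 20 of 24 sessions (83.3%), which are different thresholds for the arm mean that Table 1 defines

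*Combined protocol and SAP*

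**What the plan says.** The Feasibility Criteria paragraph in Section 3 opens with "Feasibility will be achieved if the following criteria are met" and lists five. Criterion (5) is the fidelity minimum. It asks for at least "80% of CR sessions", and the parenthesis that follows restates this as at least "20 of 24) are administered as intended for each arm (fidelity".

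Table 1 (Aim 1 Outcome Measures) lists the matching endpoint as a tertiary measure, "Mean % of CR sessions administered as intended in each arm". Its description is the percentage "of CR sessions (out of all 24 sessions) administered as intended to participants allocated to the THCR intervention" and, separately, to the traditional arm.

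Two design figures in Section 2 (Overview of Study Design) set the scale: "Each program will include 24 CR sessions over the course of 3-months", and participants are "randomized (1:1) to THCR (n=20) or traditional clinic-based CR (n=20").

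Criterion (4), adherence, has the same layout: 50% of sessions, restated as at least "12 of 24) are completed by those allocated to each arm (adherence").

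The Aim 1 Analysis paragraph treats the criteria as minimum acceptable values that inform the decision on a full trial.

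**The concern.** One criterion carries two numbers, and the plan does not say which governs. If fidelity were judged on one participant's count of sessions, the parenthesis would only restate the percentage in whole sessions. Fidelity is defined instead as an average over an arm, so the parenthesis raises the bar from 80% to 83.3%.

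At stake is the stated feasibility conclusion. Criterion (5) applies to each arm and stands alongside the other four, so missing it in either arm changes whether feasibility is reported as achieved. With no governing figure named in advance, an arm whose mean lies between the two thresholds could be reported either way.

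**Working it through.** **Inputs**

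- Percentage form of the minimum: 80% (criterion (5)).
- Count form of the minimum: 20 of 24 (criterion (5)).
- Summary measure: arm-level mean percentage, out of all 24 sessions (Table 1).
- Participants per arm: 20 (Section 2).

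**1. Reproducing the plan's figure.** 0.80 × 24 = 19.2, which rounds up to 20 whole sessions. The plan's 20 is therefore the smallest whole count that reaches 80% for one participant: 19/24 = 79.2% falls short and 20/24 = 83.3% passes. For every whole count from 0 to 24 the two forms give the same answer.

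**2. Moving to the Table 1 scale.** Planned sessions per arm: 20 × 24 = 480.

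| Form | Mean sessions per participant | Mean % | Sessions as intended, of 480 |
|---|---|---|---|
| At least 80% | 19.2 | 80.0% | 0.80 × 480 = 384 |
| At least 20 of 24 | 20 | 83.3% | 20 × 20 = 400 |

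The thresholds are 400 − 384 = 16 sessions per arm apart.

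**3. Where they disagree.** Arm totals of 384 to 399 meet the percentage form and miss the count form. That is 16 attainable totals, with means from 384/20 = 19.20 to 399/20 = 19.95 sessions, or 384/480 = 80.0% to 399/480 = 83.1%. All other totals give the same answer under both forms.

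**4. Comparison with criterion (4).** 0.50 × 24 = 12 exactly, so no arm total makes the two adherence forms disagree. The mismatch is confined to criterion (5).

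**5. How often it could matter.** The documents give no expected fidelity, so this step rests on assumed true values. The chance that one arm of 20 lands between 384 and 399 is:

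| Assumed true fidelity | Independent sessions | Within-participant correlation 0.1 | Within-participant correlation 0.3 |
|---|---|---|---|
| 75% | 0.6% | 7.6% | 12.8% |
| 80% | 49% | 36% | 25% |
| 82% | 64% | 39% | 26% |
| 84% | 31% | 29% | 22.5% |
| 90% | about 0% | 0.7% | 3.9% |

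The independent column is binomial with 480 sessions. The other two are beta-binomial simulations of 40,000 arms. The conflict is a practical matter only if true fidelity lies near the stated minimum.

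**The case against.** The best defence is that the parenthesis is only a gloss. Sessions are whole units and 20 is the right round-up. The percentage comes first in the criterion, Table 1 is on the percentage scale, and the Aim 1 Analysis computes lower limits for proportions, so most readers would apply 80%. This probably explains how the 20 arose, and it limits the severity. It does not remove the conflict, because nothing in the plan says that the percentage governs.

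A second defence is that 20 of 24 was meant as a cut-off for each participant. The Aim 2 Analysis does compare participants with high and low fidelity. But it gives no cut-off, and criterion (5) does not say what share of participants would have to reach 20. That reading would also depart from the arm mean in Table 1, so the documents do not support it.

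Three limits on weight stand. Fidelity is a tertiary measure, and the two primary measures (recruitment and THCR adherence) are untouched. The totals of 384 and 400 assume that all 480 planned sessions count; Section 3 bases quality of administration on direct observation and does not say that every session is observed. And the plan leaves another question open in the same criterion: whether the point estimate or the one-sided 95% lower limit must clear the minimum. For 480 independent sessions at 80%, those differ by about 1.645 × √(0.80 × 0.20/480) = 3.0 percentage points, close to the 3.3-point gap here. That is a separate question, and settling it would not settle this one.

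A reader might also infer that criterion (5) is an automatic go/no-go rule that a trial could pass and fail at once, or that the sponsor means to choose the figure after seeing results. The documents support neither. The criteria define feasibility, which informs a decision, and nothing suggests an intention to choose late.

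**Conclusion.** Criterion (5) is wrong as written, with minor severity. Its two forms are equivalent for one participant's whole-session count but not for the arm mean that Table 1 defines, where they lie 3.3 percentage points apart (80.0% against 83.3%).

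The consequence is confined to observed arm means of at least 80.0% and below 83.3%. The attainable range of 19.20 to 19.95 sessions assumes 20 participants in the arm and all 24 sessions counted for each. A different arm size would shift the last attainable value slightly but would not change the two thresholds. Outside this range the wording has no effect. The documents do not show that a result inside it is likely, nor which of the two figures was intended.

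**What to change.** Before results are seen, state one threshold on the Table 1 scale. For example: *mean % of CR sessions administered as intended is ≥80% in each arm*. Then delete the count in parentheses, or replace it with *a mean of 19.2 of 24*. If the stricter rule is intended, give the percentage as ≥83.3% instead. The choice is the sponsor's.

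The cost is one line of protocol wording, with no effect on conduct, data collection or sample size. The only downside is that the sponsor must commit to one figure: 80% is the easier standard by 16 sessions per arm, and 83.3% the harder.

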Aim 2 Analysis. Data from interviews will be transcribed using Microsoft Stream and I will employ thematic analysis and code for themes using a 6-phase process and NVIVO software, and adhering to the qualitative COREQ research checklists. Transcripts will be coded for barriers and facilitators to hybrid CR using the Consolidated Framework for Implementation Research (CFIR; 39 constructs within five domains [e.g., inner setting, outer setting]) and Theoretical Domains Framework (TDF; 84 theoretical constructs within 14 domains [e.g., knowledge, skills, social/professional role]). While there is considerable overlap in these theoretical frameworks, I will leverage the ways in which CFIR addresses system-level determinants and TDF addresses individual-level determinants. Two raters will review the audio and visual data for each participant. Content analysis will be used to identify patterns in the stakeholder's responses to questions about acceptability, barriers, and facilitators to THCR. I will further assess whether CR barriers and acceptability differed among those with high vs. low fidelity to THCR and among those in the THCR vs. traditional arms of the study.

**Compensation:** Participants will receive a PayCard in-person or in the mail after successfully completing the first two clinic-based CR session (CR Session 1 & 2). Once they confirm receiving the PayCard with study personnel, \$50 will be uploaded to the card as compensation for the initial clinic-based visits (payment #1). Following successful completion of CR session 12 and mid-intervention assessments, they will be compensated an additional \$50 on the PayCard (payment #2). Following successful completion of CR session 24 and post-intervention assessments, they will be compensated an additional \$50 on the PayCard (payment #3). Therefore, the total possible compensation for completing the study is \$150. All compensation is loaded onto one PayCard registered specifically to the participant.

In addition, participants enrolled in the hybrid CR program will be permitted to keep the study-provided stationary bike and adjustable ankle/wrist weights upon completion of the study, which has an estimated value of \$350.00 - \$425.00 when purchased as new.

If upon completing the study a subject indicates that they do not want to keep the study-provided equipment, the research team will offer to arrange for the bike to be picked up and donated to a charitable foundation.

Risks: There are minimal risks associated with participation in moderate-intensity bouts of physical activity including injury or medical complications. Evidence-based secondary prevention guidelines strongly recommend that post-ACS patients (including those who are at low-to-moderate risk for cardiac events) achieve ≥30 minutes of moderate aerobic activity, such as brisk walking, on ≥5 days per week within 2 weeks of hospital discharge as part of standard-of-care practice. Moreover, the American College of Cardiology/American Heart Association guidelines for the management of ACS patients recommend that all ACS patients participate in cardiac rehabilitation, which includes moderate-intensity exercise, as well as regular moderate-intensity physical activity (supervised and unsupervised). The most common injuries include muscle strains, joint sprains, and bone injuries. During moderate-intensity physical activity, heart rate and blood pressure may increase. In rare cases (risk approximately equal to one event in 60-80,000 hours of supervised patient exercise: ACSM, 2007), this can lead to a serious cardiac event. Only patients who completed their first initial clinic-based screening/evaluation visit and are deemed medically appropriate for participation will be enrolled in the study. To minimize risk, participants with high-risk features at rest and during exercise will be excluded from study participation. We will further exclude those at high-risk for adverse exercise-related cardiovascular events according to the AACVPR risk stratification criteria. Moreover, all exercise testing, prescription, and progression will be based on evidence-based guidelines that are routinely used to ensure safety in cardiac rehabilitation, and will mirror standard of care.

At the beginning of each Video Visit, we will ask the patient to provide or confirm their current physical address (e.g.. 1234 Main Street Apt. A, Small Town 10001), as well as the name and phone number of an emergency contact should they require any emergency assistance during the visit. In the case of an emergency or adverse event, we will send emergency medical services (EMS) to the physical address and contact the emergency contact. Accordingly, we will have an internal medicine physician ([name] or [name]) on-call during video visits to provide study personnel with assistance if participants experience an emergency or adverse event. In the case the participant does not answer the video call at the time of their scheduled session, a member of the research team will initiate the following steps: 1) video call through the eCC platform, and 2) phone call to the participant's preferred number. If the participant does not respond to either of these contact attempts, a member of the research team will mark the session as incomplete. In the case measurements captured by the remote devices do not populate into the eCC during partially supervised session, a member of the research team will initiate the following steps: 1) video call through the eCC platform, and 2) phone call to the participant's preferred number. If the participant does not respond to either of these contact attempts, a member of the research team will call the emergency contact. If the emergency contact cannot be contacted, a member of the research team will call the emergency contact. If the emergency contact cannot be contacted, a member of the research team will call the emergency medical services (EMS) to the participant's physical address.

Psychological Distress: The questionnaires pose modest risk of psychological discomfort. Patients may experience a range of sensations during cardiac rehab (e.g., muscle tightness, increased heart rate, shortness of breath). These symptoms are temporary, and while there is risk for experiencing these sensations, engagement in exposure techniques and physical activity is the treatment for anxiety and exercise is also critical for heart health. Thus, while intervention techniques can initially elicit possible anxiety/physical discomfort, repeated practice and engagement will actually serve to decrease anxiety and increase tolerance for exercise.

Loss of Confidentiality: A potential risk from this study is the violation of the participant's privacy, since patient medical information will be used as a source of data. We have measures in place to protect participant privacy and confidentiality.

A NYP-VCR clinical CR supervisor and physical therapist ([name]), exercise physiology scientist ([name]), and internal medicine physician ([name]) will be on-call during video visits to provide study personnel with assistance if participants experience any adverse responses to exercise during their participation in this pilot study.

**Benefits:** There is no direct benefit to subjects who participate in this study.

**Alternatives:** The alternative is not to participate. Additionally, the Principal Investigator may withdraw participants from the study after enrollment upon further examination of eligibility criteria and/or at her

professional discretion. Participants will be informed that they have the option to skip study-based questions and/or not complete all surveys. In turn, the number of skipped questions and/or incomplete surveys will become part of study analysis.

**Data and Safety Monitoring:** Data and safety monitoring will be conducted by the study staff as directed and overseen by the principal investigator. Investigators and research assistants will meet weekly to discuss any issues or concerns with the study, in particular, whether there were any unexpected complaints about the study procedures or questionnaires, or whether there were any breaches in data confidentiality (which will be reported to the IRB as required by policy). If unexpected complaints about the procedures or questionnaires are generated, then the study may be stopped or altered prior to recruiting the full sample.

